6.5.3. Vital Signs and Physical Examinations

The actual value and change from before study vaccine administration to after study vaccine administration will be summarized for each vital sign parameter: Systolic Blood Pressure, Diastolic Blood Pressure, Heart Rate, Oral Temperature, Respiratory Rate. In case of multiple measurements on Day 1 before vaccination, the closest measure from the time of vaccination will be used. In case of multiple measurements on Day 1 after vaccination, the closest measure from the time of vaccination will be used. Vital sign measurements will be presented in by-subject data listings.

Physical examination results at Baseline will be summarized. All physical examination findings will be presented in by-subject data listing.

6.6. Immunogenicity Evaluations (50 to 64 years)

All Immunogenicity summaries to be produced by treatment group, for the following:

Population: IEP, EXP

Subgroups: 50-64, 50-59, 60-64

6.6.1. GMT/GMC, GMR and GMFR

To estimate the immunogenicity response 1 month first vaccination, OPA titers (log10) and IgG titers (mcg/mL) measured at Day 29 visit will be logarithmically transformed for analysis and GMTs/GMCs will be computed with 95% CI for each assay using ANOVA and ANCOVA.

[figure not shown]
- [S] [E] First model in an ANOVA with log10-transformed concentrations/titers at Day 29 as the dependent variable and treatment group and study site as the fixed effects in the model. Bar plots of OPA GMT, IgG GMC and their 95% CI computed by this model will be created for the full IEP only.
- [S] [E] Second model in an ANCOVA with log10-transformed concentrations/titers at Day 29 as the dependent variable, treatment group and study site as the fixed effects and log10 baseline concentration/titer as the covariate

The least squares means, and their 95% CIs calculated based on the ANOVA and ANCOVA will be back transformed and reported as the group GMT and GMC values. Comparisons between relevant groups will be based on the estimated adjusted GMTs measured at Day 29 visit for 24 serotypes in VAX-24 (of those 20 in PCV20), and mean square error calculated from the basic ANOVA model using contrast statements. The main comparison of interest will be the three VAX-24 dose levels group versus the PCV20 (20 serotypes) group. However, the three VAX-24 dose groups will also be compared in a pairwise fashion on a serotype-by-serotype basis. No adjustment for multiplicity will be applied and missing data will not be imputed. GMRs will also be calculated from the ANCOVA and ANOVA models.

The analysis of GMFR at Day 29 relative to Day 1 will also be computed using similar models:

- [E] First model in an ANOVA with log10-transformed fold ratio at Day 29 as dependent variable and treatment group and study site as the fixed effects in the model. A Forest Plot summarizing the results by serotype of this model will be created for OPA on the full IEP only.
- [E] Second model in an ANCOVA with log10-transformed fold ratio at Day 29 as dependent variable, treatment group and study site as the fixed effects and log10 baseline concentration/titer as the covariate

The least squares means, and their 95% CIs calculated based on the ANOVA and ANCOVA will be back transformed and reported as the group GMFR value.

[REDACTED]

[REDACTED]

[REDACTED]

[REDACTED]

[REDACTED]

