### 5.6.3 Immune Response Assessments

Serum antibody responses to pneumococcal polysaccharides induced by vaccination will be measured using 2 standard assays, OPA and multiplexed Meso Scale Discovery (MSD).

The OPA assay has been developed and qualified by Nexelis, a GCP-compliant central laboratory, to analyze the 24 polysaccharide antigens contained in VAX-24. The OPA assay has been consistently used as the method for measuring the functional capacity of pneumococcal antibodies, as antibodies to pneumococcal PS protect the host by opsonizing pneumococci (marking pneumococci for destruction) for phagocytosis (Burton and Nahm 2006).

The MSD assay has been developed and qualified by Nexelis to measure IgG responses against the 24 polysaccharide antigens contained in VAX-24. The MSD multiplex electrochemiluminescent assay is an immunoassay platform that allows simultaneous measurement of responses against multiple antigens and has been used to evaluate responses to various pneumococcal conjugate vaccines (Marchese 2009, Goldblatt 2011, Feyssaguet 2019, and Nolan 2020).

The immune responses (as assessed by OPA and IgG assays) against the 20 polysaccharide antigens common to PCV20 and VAX-24 (1, 3, 4, 5, 6A, 6B, 7F, 8, 9V, 10A, 11A, 12F, 14, 15B, 18C, 19A, 19F, 22F, 23F and 33F) will be compared in the various treatment groups (VAX-24 at 3 different dose levels, and the comparator vaccine), and the 4 incremental polysaccharide antigens contained in VAX-24 (2, 9N, 17F and 20B) will be evaluated separately.

Immunogenicity samples will be collected for subjects aged 50 to 64 years only.

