### **9.7 Immunogenicity Analysis (50 to 64 years)**

#### **9.7.1 GMT/GMR**

Immunogenicity analyses will be performed by age group (50 to 59 and 60 to 64) and overall (50 to 64 years). Analyses will be performed for both OPA titers ( $\log_{10}$ ) and IgG titers (mcg/mL). All immunogenicity analyses will be based on the IEP and Exposed Population.

The GMTs and GMCs will be analyzed via linear models. The primary model is an analysis of variance (ANOVA), with logarithmically-transformed titers ( $\log_{10}$ ) as the dependent variable and treatment group and study site as the fixed effects in the model. The results included in the main tables of this report will be based on this basic ANOVA model. As a secondary analysis, in order to remove the effect of baseline concentration on the GMTs, an analysis of covariance (ANCOVA) will also be performed. The ANCOVA includes treatment group and study site as the fixed effects and  $\log_{10}$  baseline titer as the covariate in the model. The rationale for including

baseline values as a covariate is that prior data have shown vaccine response is correlated with baseline antibody levels.

The least squares means and their 95% confidence intervals (CIs) calculated based on the ANOVA and ANCOVA will be back transformed and reported as the group GMT and GMC values (adjusted for the mean baseline in the case of the ANCOVA). GMRs will also be calculated from the ANCOVA and ANOVA models.

Comparisons between relevant groups will be based on the estimated adjusted GMTs measured at Day 29 for 24 serotypes in VAX-24 (of those 20 in PCV20), and mean square error calculated from the basic ANOVA model using contrast statements. The analysis of GMFR relative to Day 1 will also be computed using similar models.

The main comparison of interest will be the three VAX-24 dose levels group versus the PCV20 (20 serotypes) group. However, the three VAX-24 dose groups will also be compared in a pairwise fashion on a serotype by serotype basis. No adjustment for multiplicity will be applied and missing data will not be imputed.

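### The error term for the GMT contrasts is loosely specified: it may not come from the same model as the means, and for serotypes 2, 9N, 17F and 20B it pools in an arm that received no antigen

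*SAP*

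**What the plan says.** Protocol 9.7.1 states: "Comparisons between relevant groups will be based on the estimated adjusted GMTs measured at Day 29 for 24 serotypes in VAX-24". The same sentence, repeated almost unchanged in SAP 6.6.1, takes the error from the "mean square error calculated from the basic ANOVA model using contrast statements".

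Two models are specified for log10 Day 29 values. The basic ANOVA has treatment group and site as fixed effects. The ANCOVA has "treatment group and study site as the fixed effects and log10 baseline concentration/titer as the covariate". Both documents report least squares means and 95% intervals from each model, and SAP 6.6.1 adds: "GMRs will also be calculated from the ANCOVA and ANOVA models". Protocol 9.7.1 makes the ANOVA primary and bases the main tables on it. SAP 6.6.1 lists a first and a second model without repeating that ranking.

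On scope, SAP 6.6.1 says: "The main comparison of interest will be the three VAX-24 dose levels group versus the PCV20 (20 serotypes) group". It also requires pairwise comparison of the three VAX-24 doses, serotype by serotype. Protocol 5.6.3 says that "the 4 incremental polysaccharide antigens contained in VAX-24 (2, 9N, 17F and 20B) will be evaluated separately". Neither document says in its visible text that the PCV20 arm leaves the model for those four serotypes, or how unequal variances would be handled.

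**The concern.** A contrast has a valid standard error when the estimate and the residual variance come from the same fitted model and that variance describes the arms being compared. The contrast sentence leaves both conditions open.

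On the first, protocol 9.7.1 attaches baseline adjustment to the ANCOVA, so a programmer may take *adjusted GMTs* to be ANCOVA means and then follow the instruction to use the ANOVA error. Another may take them to be ANOVA least squares means. Both would be following the text, and their intervals would differ.

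On the second, PCV20 recipients get no antigen for 2, 9N, 17F and 20B, so their Day 29 values mostly reflect pre-existing antibody. SAP 5.2 sets results below the LLOQ to half the LLOQ for GMTs and to the LLOQ for fold ratios. A PCV20 subject below the limit at both visits therefore has a fold ratio of exactly 1. This gives a reason to expect a different spread in that arm, in the GMT models and in the GMFR models, which SAP 6.6.1 describes as similar.

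At stake are the intervals that compare VAX-24 doses on the four serotypes the vaccine adds, in a study whose title calls it dose-finding.

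**Working it through.** The documents give no standard deviation, interval width or power for these contrasts, so there is no stated figure to reproduce. The baseline correlation and the variance ratio below are assumptions, shown as ranges.

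**Inputs from the documents.** 200 subjects per arm, 1:1:1:1 (SAP 2.3); two-sided 0.05 level (SAP 6.2.1); about 10 sites (protocol synopsis); site as a fixed effect (SAP 6.6.1).

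**Step 1: ANCOVA means with the ANOVA error.** With baseline correlation ρ, the ANCOVA residual variance is (1 − ρ²) times the ANOVA residual variance. The interval is therefore too wide by the factor 1/√(1 − ρ²), and coverage is 2Φ(1.96 × factor) − 1.

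| Assumed ρ | Width factor | Coverage |
|---|---|---|
| 0.2 | 1.02 | 95.4% |
| 0.3 | 1.05 | 96.0% |
| 0.5 | 1.15 | 97.6% |
| 0.6 | 1.25 | 98.6% |
| 0.7 | 1.40 | 99.4% |

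For example, at ρ = 0.5: 1/√0.75 = 1.155.

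**Step 2: one variance pooled over four arms.** Set the VAX-24 variance to 1 and the PCV20 variance to r. With equal arms the mean square error estimates (3 + r)/4.

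- Dose versus dose: the correct variance is proportional to 2 and the one used to 2(3 + r)/4, so the width factor is √[(3 + r)/4].
- Dose versus PCV20: the correct variance is proportional to 1 + r, so the width factor is √[2 × ((3 + r)/4)/(1 + r)].

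| Assumed r | Dose vs dose: factor (coverage) | Dose vs PCV20: factor (coverage) |
|---|---|---|
| 0.5 | √0.875 = 0.935 (93.3%) | √(1.75/1.5) = 1.080 (96.6%) |
| 1 | 1.000 (95.0%) | 1.000 (95.0%) |
| 2 | √1.25 = 1.118 (97.2%) | √(2.5/3) = 0.913 (92.6%) |

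A more extreme assumption, PCV20 SD half the VAX-24 SD (r = 0.25), gives √0.8125 = 0.901 and 92.3% coverage for dose versus dose.

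**Step 3: simulation.** Four arms of 200, 10 sites, 4,000 runs per case.

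- Equal variances, each model with its own error: coverage 94.7% to 95.3% (ANOVA) and 94.9% to 95.4% (ANCOVA).
- ANCOVA means with ANOVA error, ρ = 0.5: 97.4% and 97.8% for the two contrast types, against 97.6% by formula.
- PCV20 SD half the VAX-24 SD, ANOVA: dose-versus-dose coverage 92.5%, against 92.3% by formula. Using the ANCOVA with its own error in the same setting gave 92.4%.

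The last result shows that matching model and error does not cure unequal variances. The two parts need separate remedies.

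**The case against.** A reader might infer that these confidence intervals are simply wrong. The documents do not support that, for four reasons.

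- *Adjusted* has an innocent reading. ANOVA least squares means are adjusted for site, and a contrast statement in a fitted ANOVA uses that model's own estimates and error. SAP 5.2 defines GMT and GMR from the least squares means of the model, GMRs come from both models, and the protocol's main tables rest on the ANOVA. This objection stands. What remains is that the SAP does not say which reading is meant. On the less favourable one, the intervals only lose precision.
- A pooled mean square error is the standard ANOVA error term and is exact under equal variances. No arm variance appears in the documents, and the error could run in either direction. This also stands. The BLQ rule and the missing antigen are reasons to guard against unequal variances; they do not show that variances differ.
- The scope is limited. The main PCV20 comparison covers the 20 shared serotypes, and for the other four protocol 9.7.2 compares doses with PCV20 by logistic regression on a 4-fold OPA rise, which uses no mean square error. That largely removes the dose-versus-PCV20 concern. It does not remove the dose-versus-dose contrasts, which are required for each serotype.
- The consequence is modest. These endpoints are secondary or exploratory, and the visible text sets no GMR success margin and ties no dose choice to these intervals.

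SAP text after 6.6.1 is redacted and may say more. It is not counted as missing. Nor does the plan say that the error is pooled across serotypes; that should not be read into it.

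**Conclusion.** The point holds as a gap in specification with a bounded effect. If the contrasts pair baseline-adjusted means with ANOVA error, intervals are too wide, by about 5% at ρ = 0.3 and 15% at ρ = 0.5. If the means are site-adjusted ANOVA means, there is no error. Protocol 9.7.1 says response correlates with baseline but gives no value, so ρ is assumed.

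For dose-versus-dose contrasts on 2, 9N, 17F and 20B, the pooled variance can mislead either way: 6.5% too narrow with 93.3% coverage at an assumed variance ratio of 0.5, and 12% too wide at a ratio of 2. At a ratio of 1 the intervals are exact. The narrow direction is the one that matters, because it overstates differences between doses. The change is worth making because it keeps the intervals approximately valid whichever way the variances fall, at almost no cost.

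**What to change.** In SAP 6.6.1, with protocol 9.7.1 aligned:

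1. Define *adjusted GMT*, and state that each contrast and its standard error come from the same fitted model: ANOVA contrasts with ANOVA error, ANCOVA contrasts with ANCOVA error.
2. For serotypes 2, 9N, 17F and 20B, in the GMT, GMC and GMFR models, either estimate a residual variance per arm with Satterthwaite degrees of freedom (in SAS, PROC MIXED with REPEATED / GROUP=treatment), or fit dose-versus-dose contrasts without the PCV20 arm. Name one of these before the Day 29 interim database lock.

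The cost is wording and one programming option. Omitting PCV20 loses some error degrees of freedom. At full enrolment with 10 sites, the ANOVA falls from 800 − 4 − 9 = 787 to 600 − 3 − 9 = 588, and the t multiplier moves from 1.963 to 1.964. In the 60 to 64 stratum at its minimum of 25 per arm, it falls from 100 − 13 = 87 to 75 − 12 = 63, and the multiplier moves from 1.988 to 1.998, or about 0.5%.

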7. CHANGES TO PLANNED ANALYSES

As of this date, there have been no changes between the protocol-defined statistical analyses and those presented in this statistical plan.

9. APPENDICES

9.1. Schedule of Assessments

APPENDIX A: SCHEDULE OF EVENTS

Study Event	Visit Number:	–	01	02	03	04	05 - 08	–
	Study Visit:	Screening	Day 1	Day 8	Day 15 (Phone)	Day 29	Months 3, 4, 5, 6 (Phone)	Early Termination
	Window:	-30d		+3d	+3d	±3d	±5d	
Informed Consent		X						
Demographics, Medical History		X	X ^a					
Concomitant Medications		X	X	X	X	X ^c	X ^c	
Physical Exam(s), targeted		X	X ^a					
Vital Signs		X	X ^b					
Confirmation of Eligibility		X	X					
Randomization			X					
Study Vaccine Administration			X					
Post-vaccination Observation (at least 30 min)			X					
Issue e-Diary instructions, Ruler, Thermometer, Conduct Training			X					
Review e-Diary Data				X				
AE Evaluation (Solicited and/or Unsolicited)			X	X	X	X	X ^c	
Clinical Labs ^d								
Hematology, Chemistry, Urinalysis Tests		X				X		
Pregnancy Tests (Urine or Serum) ^e		X	X					
HIV EIA, HBsAg, HCV Ab		X						
Serum for Immunogenicity, [REDACTED] (50 to 64 yo only)			X			X		

Refer to
Protocol for
Procedures

Abbreviations: AE = adverse event; HBsAg = Hepatitis B surface antigen; HCV = Hepatitis C virus antibody, HIV EIA = human immunodeficiency virus, enzyme immunoassay; [REDACTED] SAE = serious adverse event; yo = years old

^aConduct or collect prior to study vaccination (if indicated by updated medical history or change in health status, as applicable)

^bVitals to be taken prior and after study vaccine administration (≥ 30 min)

^cNew onset of chronic illnesses, MAAEs and SAEs, and associated concomitant medications collected after Day 29

^dAll samples collected prior to study vaccine administration

^eSerum pregnancy test at Screening and urine pregnancy test prior to vaccine administration
